12.4.2 UNANTICIPATED ADVERSE EVENT REPORTING

The investigator site will report unanticipated AEs to the reviewing Institutional Review Board (IRB) and the sponsor/CRO. The unanticipated AE report will include the following information:

- Protocol identifying information: protocol title and number, PI's name, and the IRB project number;
- A detailed description of the event, incident, experience, or outcome;
- An explanation of the basis for determining that the event, incident, experience, or outcome represents an unanticipated AE;
- A description of any changes to the protocol by the sponsor/CRO or other corrective actions that have been taken or are proposed in response to the unanticipated AE.
- The sponsor/CRO will update the IB or provide Dear Doctor letter should these actions be deemed required.

To satisfy the requirement for prompt reporting, unanticipated AEs will be reported using the following timeline:

- Unanticipated AEs that are fatal and life-threatening SAEs will be reported to the IRB and to the sponsor/CRO within seven (7) days of the PI becoming aware of the event.
- Any other unanticipated AEs that are SAEs will be reported to the IRB and to the sponsor/CRO within 15 days of the PI becoming aware of the problem.
- All unanticipated AEs that non-serious AEs are not required to be reported to the IRB or to the sponsor/CRO.
- All unanticipated SAEs should be reported to appropriate institutional officials (as required by an

institution's written reporting procedures), the supporting agency head (or designee), and the OHRP if applicable.

- All SUSARs will be reported in compliance with the requirements of the respective Regulatory Authority.

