12.3.1.2.3 CLASSIFICATION OF AN ADVERSE EVENT

Severity of Event

The PI is responsible for evaluating all AEs and determining the severity of the event. Severity will be categorized as mild, moderate or severe according to the following definitions:

- **Mild:** Event may be noticeable to subject; does not influence daily activities; usually does not require intervention
- **Moderate:** Event may be of sufficient severity to make subject uncomfortable; performance of daily activities may be influenced; intervention may be needed
- **Severe:** Event may cause severe discomfort; usually interferes with daily activities; subject may not be able to continue in the trial; treatment or other intervention usually needed

Relationship to Study Intervention

Relationship of an AE to IP will be assessed by the PI as follows:

- **Definite:** There is a clinically plausible time sequence between the onset of the AE and the administration of IP; when the event responds to withdrawal of IP and/or recurs with re-administration of IP
- **Probable:** There is a clinically plausible time sequence between the onset of the AE and the administration of IP; the AE is unlikely to be caused by the concurrent/underlying illness, other drugs or procedures
- **Possible:** There may or may not be a clinically plausible time sequence between the onset of the AE and the administration of IP and a cause cannot be ruled out
- **Unrelated:** There is not a temporal or causal relationship to IP administration

Expectedness

The medical monitor and sponsor/CRO will be responsible for determining whether an AE is expected or unexpected. An AE will be considered unexpected if the nature, severity, or frequency of the event is not consistent with the risk information previously described for the study intervention. Expectedness is further defined in the Investigator's Brochure (IB) under Anticipated Risks and Side Effects. The list of AEs found in the IB can be considered to be expected AEs.

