12.4 UNANTICIPATED ADVERSE EVENTS

12.4.1 DEFINITION OF UNANTICIPATED ADVERSE EVENTS

The Office for Human Research Protections (OHRP) considers unanticipated problems involving risks to subjects or others to include, in general, any incident, experience, or outcome that meets all of the following criteria:

- Unexpected in terms of nature, severity, or frequency given (a) the research procedures that are described in the protocol-related documents, such as the Institutional Review Board (IRB)-approved research protocol and informed consent document; and (b) the characteristics of the subject population being studied;
- Related or possibly related to participation in the research (“possibly related” means there is a reasonable possibility that the incident, experience, or outcome may have been caused by the procedures involved in the research); and
- Suggests that the research places subjects or others at a greater risk of harm (including physical, psychological, economic, or social harm) than was previously known or recognized

The sponsor/CRO will comply with these criteria for reporting unanticipated AEs.

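### Protocol 12.4.2 requires sites to report unanticipated AEs, then exempts all non-serious ones, although the definition in 12.4.1 has no seriousness criterion

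*Protocol*

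**What the plan says.** Protocol 12.4.1 sets three criteria, all of which must be met:

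- "Unexpected in terms of nature, severity, or frequency given" the research procedures and the population studied;
- "Related or possibly related to participation in the research";
- "Suggests that the research places subjects or others at a greater risk of harm" than was previously known.

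The section ends with a commitment: "The sponsor/CRO will comply with these criteria for reporting unanticipated AEs".

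Protocol 12.4.2 begins with a duty on the site that has no seriousness limit: "The investigator site will report unanticipated AEs to the reviewing Institutional Review Board (IRB) and the sponsor/CRO". It then lists deadlines. The first reads "Unanticipated AEs that are fatal and life-threatening SAEs will be reported to the IRB and to the sponsor/CRO within seven (7) days" of the investigator becoming aware. The second gives 15 days for other unanticipated AEs that are SAEs. The third bullet is the exemption: "All unanticipated AEs that non-serious AEs are not required to be reported to the IRB or to the sponsor/CRO". It lacks a verb, but it plainly means unanticipated AEs that are non-serious.

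Expectedness is assigned elsewhere. Protocol 12.3.1.2.3 states: "The medical monitor and sponsor/CRO will be responsible for determining whether an AE is expected or unexpected".

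**The concern.** The exemption does not cover ordinary non-serious AEs. It covers events already classed as unanticipated, and so already judged unexpected, possibly related and pointing to more risk than was known. Those are the events the definition exists to bring forward. A site reading 12.4.2 cannot tell whether the opening sentence or the bullet governs.

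The roles do not connect either. Unexpectedness is the first criterion in 12.4.1, and 12.3.1.2.3 gives that judgement to the medical monitor and sponsor/CRO. Yet the bullet tells the site that it need not notify the sponsor/CRO of the event.

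At stake is the time it takes for a new, non-serious, possibly drug-related finding to reach those who can act on it, and whether an IRB hears of it at all. The primary efficacy analysis is not affected.

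**Working it through.** The plan gives no figure to reproduce on this point. The check compares the definition, the reporting rule and every other readable AE reporting route.

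**1. Does the definition depend on seriousness?** No. None of the three criteria in 12.4.1 mentions it, and the closing commitment adds no such limit.

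**2. Does 12.4.2 agree with the definition?** The opening duty does. The two deadlines (7 and 15 days) apply to SAEs only. The third bullet removes non-serious events from both recipients. A later bullet on institutional officials and federal oversight also concerns serious events only.

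**3. Does another section supply the missing route?**

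| Protocol section | What it covers | Sends a non-serious unanticipated AE to the IRB? | Gives the sponsor prompt notice of it? |
|---|---|---|---|
| 12.3.1.1 | Investigator reports SAEs to the IRB | No | No |
| 12.3.1.2.4 and 12.3.1.2.5 | All AEs recorded on source documents and CRFs | No | No deadline for non-serious AEs |
| 12.3.1.2.6 | SAE reporting by site and sponsor | No | No |
| 12.3.1.2.7 | SAEs at or after the last contact; medical monitor told of clinically significant trial-related abnormalities at the end of the trial | No | Only at the end of the trial |
| 14.1.5 | DMC evaluates available safety data at charter times | No | No |
| 14.1.7.1.1 | Data forwarded to the sponsor/CRO, at the latest when the study terminates | No | Outer limit only |

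Apart from the opening sentence of 12.4.2, which the bullet contradicts, no readable provision sends such an event to an IRB. None sets a prompt deadline for telling the sponsor.

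**4. Would a single site notice a pattern unaided?** This is an illustration; the conclusion does not depend on it. About 150 subjects at about 20 sites gives 150/20 = 7.5 per site. Assume equal-sized sites and events falling at random. The documents give no rate for such events, so 2 to 4 events are assumed.

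- 2 events (2/150 = 1.3%): probability that both are at different sites = 142.5/149 = 0.96.
- 3 events (3/150 = 2.0%): (142.5/149) × (135/148) = 0.87.
- 4 events (4/150 = 2.7%): (142.5/149) × (135/148) × (127.5/147) = 0.76.

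Over this range each site would usually see at most one event. Recognising a pattern therefore depends on pooled data, and the bullet requires no expedited notice to the party that pools them.

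**The case against.** The best defence is that these events are captured and reviewed. Every non-serious AE goes on the CRF with severity and relationship (12.3.1.2.4), and clinically significant changes on examination must be recorded as AEs (12.3.1.2.1). The sponsor/CRO and the DMC pool data across sites, and both have access to non-serious AEs. The end-of-study limit in 14.1.7.1.1 is an outer bound and does not show that data will arrive late. The important-medical-event criterion in 12.3.1.2.2 moves some worrying events into the SAE route. All of this stands, and it narrows the gap for the sponsor. It gives the IRB no route.

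A second defence is that the bullet sits in a list about prompt reporting, so it may limit expedited reports only and leave the opening duty in force. That reading is possible, but the bullet's wording is not limited to timing. Even on that reading, sites have a duty with no deadline.

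A reader might infer more than the documents support:

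- *That these events have no reporting route at all.* The CRF and DMC routes exist. What is missing is prompt notice to the sponsor and any notice to an IRB.
- *That the sponsor is released from its commitment in 12.4.1.* The bullet relieves the site of a separate report; the sponsor's commitment remains.
- *That consent updates in 12.4.2 would be missed.* That section names protocol changes, corrective actions, an Investigator's Brochure update and a Dear Doctor letter. It names no consent update, and it does not make the brochure update or letter depend on a site's report.
- *That toxin-related signals in particular are lost.* The bullet names no event type. A mild unexpected symptom qualifies only if it also suggests greater risk than was known. Redacted text after 12.3.1.2.7 and in SAP 6.12.1 could contain a rule for particular events.

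**Conclusion.** The contradiction is real and rests on readable text: the bullet conflicts with the opening sentence of 12.4.2 and with the definition and commitment in 12.4.1. If followed, it leaves a small class of events, non-serious but meeting all three criteria, with no readable route to an IRB. The sponsor receives them on the ordinary CRF timetable and the DMC at charter times.

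The size is best stated by count. None of the three criteria requires seriousness, both deadlines in 12.4.2 are limited to SAEs, and no readable provision outside 12.4.2 brings such an event to an IRB. The number of events is unknown and probably small, because all three criteria must be met. The conclusion assumes that no redacted passage supplies the route; even if one did for particular events, the conflict between 12.4.1 and 12.4.2 would remain. The protocol should be corrected, but the defect is moderate because recording and pooled review are in place.

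**What to change.** Delete the third deadline bullet in 12.4.2 and reconcile 12.3.1.2.3, 12.4.1 and 12.4.2 in the same amendment, with these steps:

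1. The site promptly notifies the sponsor/medical monitor, within a time stated in the protocol, of any non-serious AE that it considers possibly related and suggestive of greater risk than was previously known.
2. The sponsor/medical monitor determines expectedness, as 12.3.1.2.3 already provides.
3. Events confirmed to meet all three criteria in 12.4.1 are reported to the IRB within a stated time.
4. All other non-serious AEs stay on the CRF route only.

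The order matters. If sites had to apply all three criteria before notifying anyone, they would have to decide unexpectedness, which the protocol assigns to the party being notified.

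The cost is a short protocol amendment, a line in site training and a few extra reports. No change to the statistical analysis is needed.

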12.4.3 REPORTING UNANTICIPATED ADVERSE EVENTS TO SUBJECTS

The sponsor/CRO will disclose clinical study data to individuals, to investigator sites, and publicly as aggregate summaries, in accordance to Regulatory and local legal requirements.

13 STATISTICAL CONSIDERATIONS

13.1 SAMPLE SIZE DETERMINATION

The sample size calculations are based on the minimal clinically important difference of 2 points for NPRS ([Farrar, 2001](#); [Michener, 2011](#)). [REDACTED]

13.2 POPULATIONS FOR ANALYSES

Approximately 150 subjects, 18 to 65 years of age, will be randomized [REDACTED]

- **Intent-to-Treat (ITT) Population:** Efficacy analysis will be performed using the ITT population, which includes all subjects randomized who received study treatment, with treatment arms classified based on randomization assignment, regardless of the actual treatment received.

[REDACTED]

[REDACTED]

[REDACTED]

[REDACTED]

[REDACTED]

[REDACTED]

13.3 STATISTICAL ANALYSES

13.3.1 GENERAL CONSIDERATIONS

[figure not shown]
All evaluable efficacy data will be included in the analysis following the ITT principle.

13.3.2 ANALYSIS OF THE PRIMARY EFFICACY ENDPOINT

The primary endpoint is:

- Change from baseline in the NPRS score, which is recorded within 15 minutes after stepping out of bed in the morning and averaged over 5 days (defined as 4 days prior to the study visit and on the study visit day) at Week 8. For the primary analysis, missing data will be imputed by the multiple imputation approach. Analysis of covariance (ANCOVA) model will be used, including investigator site and treatment group as factors, and baseline NPRS score as a covariate.

Analysis of the primary efficacy endpoint will be based on the ITT or treatment policy estimand and is fully defined in the Statistical Analysis Plan (SAP).

Laboratory results and vital sign data will be summarized by visit and treatment arm, using descriptive

[REDACTED]

[REDACTED]

[REDACTED]

[REDACTED]

[REDACTED]

[REDACTED]

[REDACTED]

[REDACTED]

[REDACTED]

[REDACTED]

[REDACTED]

[REDACTED]

[REDACTED]

[REDACTED]

[REDACTED]

[REDACTED]

[REDACTED]

[REDACTED]

[REDACTED]

[REDACTED]

13.3.11 SUB-GROUP ANALYSES

Sub-group analysis will be presented in the SAP, if appropriate.

13.3.12 TABULATION OF INDIVIDUAL SUBJECT DATA

Individual subject data will be listed by measure and time point at completion of the study.

14 SUPPORTING DOCUMENTATION AND OPERATIONAL CONSIDERATIONS

14.1 REGULATORY, ETHICAL, AND STUDY OVERSIGHT CONSIDERATIONS

14.1.1 INFORMED CONSENT PROCESS

14.1.1.1 INFORMED CONSENT AND AUTHORIZATION TO RELEASE HEALTH INFORMATION

Written informed consent will be obtained from all subjects before any study-related procedures (including any screening procedures) are performed. The PI may discuss the study and the possibility for entry with a potential subject without first obtaining consent. However, a subject wishing to participate must give written informed consent prior to any study-related procedures being conducted, including those performed solely for the purpose of determining eligibility for study participation, and including withdrawal from current medication (if required prior to study entry). The PI has both the ethical and legal responsibility to ensure that each subject being considered for inclusion in this study has been given a full explanation of the procedures and expectations for study participation.

Investigator site-specific informed consent form templates must be forwarded to the sponsor/CRO for approval prior to submission to an IRB/Independent Ethics Committee (IEC) that is registered with the US Department of Health and Human Services (HHS) or applicable health authority. Each subject will sign the consent form that has been approved by the same IRB/IEC that was responsible for protocol approval. Each informed consent document must adhere to the ethical principles stated in the Declaration of Helsinki and will include the elements required by FDA regulations in 21 CFR Part 50, as well as the elements required by the ICH GCP guideline, and applicable federal and local regulatory requirements. The consent form must also include a statement that the sponsor/CRO, their designees, and auditing regulatory agencies will have direct access to the subject's records and medical history for study related purposes.

Once the appropriate essential information has been provided to the subject and fully explained by the PI (or a qualified designee) and it is felt that the subject understands the implications and risks of participating in the trial, the IRB/IEC approved consent document shall be signed and dated by both the subject and the person obtaining consent (PI or designee), and by any other parties required by the IRB/IEC or other regulatory authorities. The subject will be given a copy of the signed informed consent document with the original maintained in the blinded ISF by the PI. All of the above activities must be completed before any study related procedures are conducted (including any screening study procedures).

14.1.1.2 CONSENT PROCEDURES AND DOCUMENTATION

Informed consent is a process that is initiated prior to the individual's agreeing to participate in the study and continues throughout the individual's study participation. Consent forms will be IRB-approved and the subject will be asked to read and review the document. The PI will explain the research study to the subject and answer any questions that may arise. A verbal explanation will be provided in terms suited to the subject's comprehension of the purposes, procedures, and potential risks of the study and of their rights as research subjects. Subjects will have the opportunity to carefully review the written consent form and ask questions prior to signing. The subject should have the opportunity to discuss the study with their family or surrogates or think about it prior to agreeing to participate. The subject will sign the informed consent document prior to any procedures being done specifically for the study. Subjects must be informed that participation is voluntary and that they may withdraw from the study at any time, without prejudice. A copy of the informed consent document will be given to the subjects for their records. The informed consent process will be conducted and documented in the source document (including the date), and the form signed, before the subject undergoes any study-specific procedures. The rights and welfare of the subjects will be protected by emphasizing to them that the quality of their medical care will not be adversely affected if they decline to participate in this study.

[figure not shown]
14.1.1.3 STUDY DISCONTINUATION AND CLOSURE.

This study may be temporarily suspended or prematurely terminated if there is sufficient reasonable cause. Written notification, documenting the reason for study suspension or termination, will be provided by the suspending or terminating party to subjects, investigator sites, the IND sponsor and regulatory authorities. If the study is prematurely terminated or suspended, the PI will promptly inform subjects, the IRB, and sponsor/CRO and will provide the reason(s) for the termination or suspension. Subjects will be contacted, as applicable, and be informed of changes to study visit schedule.

Circumstances that may warrant termination or suspension include, but are not limited to:

- Determination of unexpected, significant, or unacceptable risk to subjects
- Insufficient compliance to protocol requirements
- Data that are not sufficiently complete and/or evaluable
- Determination of futility

The study may resume once concerns about safety, protocol compliance, and data quality are addressed, and satisfy the sponsor/CRO, IRB and/or FDA.

[REDACTED]

[REDACTED]

[REDACTED]

[REDACTED]

[REDACTED]

[REDACTED]

[REDACTED]

[figure not shown]
[figure not shown]
[REDACTED]

14.1.5 SAFETY MONITORING/DATA MANAGEMENT

An Independent Data Monitoring Committee (DMC) will be appointed to review safety data during the study. Details of the composition and scope of the committee's mandate will be presented in a DMC charter document. The DMC will evaluate all safety data available at timepoints specified in the charter and will make appropriate recommendations.

14.1.6 MONITORING, COMPLIANCE, AND QUALITY

All aspects of the study will be monitored by the sponsor/CRO according to GCP and SOPs for compliance with applicable government regulations, (i.e., Informed Consent Regulations and Institutional Review Board regulations).

14.1.7.1 DATA COLLECTION AND MANAGEMENT RESPONSIBILITIES

14.1.7.1.1 DATA COLLECTION

For this trial, all protocol-specified data recorded in the source documents will be entered on the CRFs from the source documents. Subject assessments will be completed by the individual subjects directly on the corresponding CRFs. In addition to signature confirmation that a subject meets the study eligibility criteria, upon each subject's completion of the trial, the PI will sign a statement indicating that all pages of the subject's case report have been reviewed. Signature stamps and "per signatures" are not acceptable.

It is the sponsor/CRO's policy that the study data be verifiable with the source data that necessitates access to all original recordings, laboratory reports, and other records for each subject. The PI must therefore agree to allow access to subjects' records, and source data must be made available for all study data. Subjects (or their legal representatives) must also allow access to their medical records. Subjects will be informed of the importance of increased record access and permission granted by signature on the informed consent document prior to Screening.

Checks will be performed to ensure the quality, consistency, and completeness of the data. Instances of missing or un-interpretable data will be resolved with the PI or Study Coordinator. Data queries will be sent to the investigator site. Investigator site staff will be responsible for providing resolutions to the data queries and for correcting the CRFs, as appropriate.

The PI must keep written or electronic source documents for every subject participating in the clinical study. Source documentation must include subject demographic and medical information including but not limited to:

- Date of birth
- Sex
- Race
- Ethnicity
- Medical history
- Comorbid conditions
- Concomitant therapies/medication
- Study visit dates
- Performed examinations, evaluations, and clinical findings
- IP administration
- AEs, SAEs, or pregnancy (as applicable)

Additionally, any other documents with source data, especially original printouts of data that were generated by technical equipment must be included in the subject's source document (e.g., laboratory value listings). All these documents must have at least the subject's initials, study number, and the date of the evaluation.

The data recorded during the course of the study will be documented in the CRF and/or the trial-specific forms. Before or at study termination, all data must be forwarded to the sponsor/CRO. The data will then be recorded, evaluated, and stored in anonymous form in accordance with data-protection regulations.

Subjects will authorize the use of their protected health information during the informed consent process in accordance with the applicable privacy requirements. Subjects who deny permission to use and disclose protected health information will not be eligible to participate in the study. The PI will ensure that the study documents forwarded to the sponsor/CRO, and any other documents, contain no mention of subject names.

Any amendments and corrections necessary will be undertaken in both the source documents and CRFs (as appropriate) and countersigned by the PI, or documented designee, stating the date of the amendment/correction. Errors must remain legible and may not be deleted with correction aids. The PI must state his/her reason for the correction of any data. In the case of missing data/remarks, the entry spaces provided in the CRF should be cancelled out so as to avoid unnecessary follow-up inquiries.

Regulatory authorities, the IRB/IEC and/or the sponsor/CRO's Quality Assurance group (or designee) may request access to all source documents, CRFs, and other study documentation for on-site audit or inspection. The PI must guarantee direct access to these documents. CRFs will be kept by the sponsor/CRO or an authorized designee in a secured area. Clinical data will be recorded in a computer format for subsequent statistical analyses. Data files will be stored on electronic media with a final master data file kept by the sponsor/CRO after descriptive and statistical analyses and reports have been generated and are complete.

